The proposed research is a low-risk behavioral trial. Study staff will be available to participants who have any difficulty with their equipment or any unexpected reaction during the intervention period. Study staff will be required to report all serious adverse events (SAEs) to the Mount Sinai IRB according to policies and procedures outlined by that body. Study staff members are also responsible to report all SAEs to the study PI as well. As per Icahn School of Medicine at Mount Sinai's IRB policies, the study PI is required to notify the IRB promptly of any unanticipated problems involving SAEs and risks to subjects or others that occur. The study staff PIs will monitor the progress of the trial and safety of participants on an ongoing basis. The procedures of this study will ensure discussion and reporting of all possible outcomes including adverse events. If the adverse event is due to the intervention and is unexpected, the PI will draft a safety report and send a copy to the Mount Sinai IRB. The IRB committee will serve as an objective review mechanism. This policy/procedure means that any potential conflict of interest inherent in the PI being the sole reviewer of SAEs is avoided.

We will use screening procedures from our prior grants to assess depression/suicidality. If risk of suicidality or severe depression is revealed, a licensed clinical psychologist in New York State, will contact the participants the same day, taking emergency steps and making referrals as needed.

2. Plans for assuring adherence with requirements regarding the reporting of adverse events (AEs).

All serious AEs (e.g., medical occurrences resulting in either hospitalization or death) that occur during the study defined by the given protocol, regardless of the relation to the research, must be reported to the IRB by telephone, e-mail or fax within 24 hours of the investigator's awareness of the occurrence of the

	Protocol Name:	Systematic Programmed Illumination of Hospital Rooms to Prevent/Reduce Cancer-Related Fatigue during Autologous Stem Cell Transplantation for Multiple Myeloma
	Principal Investigator:	[name]; [contact]
	Primary Contact Name/Contact Info:	[name], [contact], [contact]
	Date Revised:	8/15/2019
	Study Number:	IF# 2517160 HS# 15-00777 GCO#: 15-2009

event. The PI will report SAEs to the Mount Sinai IRB and will disseminate information to other sites or agencies as necessary. These safety reports are a written account of an SAE determined by the PI to be both related to the psychological treatment under investigation and unexpected in nature. Serious AEs will be summarized annually in the IRB application for continuation or termination of research.

All expected non-serious AEs that occur at a greater frequency or severity than anticipated and all unexpected non-serious AEs will be reported to the Mount Sinai IRB within 15 working days of the PI becoming aware of the event. Adverse events that will be reported include suicidal ideation, which will be monitored at each check-in. These AEs are also summarized annually in the IRB application for continuation or termination of the research.

3. Plans for assuring that any action resulting in a temporary or permanent suspension of an NCI-funded clinical trial is reported to the NCI grant program director responsible for the grant.

The Director of the Grants and Contracts Office at Icahn School of Medicine at Mount Sinai will provide prompt written notification of any action resulting in a temporary or permanent suspension of this protocol to the NCI grant program director responsible for the grant.

4. Plans for assuring data accuracy and protocol adherence.

Data that will be collected from study participants will be in the form of self-report measures, actigraphy data, urine collection, and information from Daysimeter light monitors. These measures will generate information concerning: 1) fatigue; 2) sleep patterns; 3) depression; 4) biological mediators of the investigated symptoms; 6) general quality-of-life and information on common cancer treatment-related sequelae; and 5) socio-demographic and medical variables. The study PI and research team will assess data from sleep journals and Actigraphs as indicators of protocol adherence. The research team will have conference calls as stated above to monitor any adherence or accuracy problems that may arise in the course of the study. To ensure the validity and integrity of study data, a research coordinator will be blinded to the treatment assignment. The blinded research coordinator will oversee data management responsibilities (e.g., data entry and data checking) while the unblinded research coordinator will oversee the active and comparison light intervention. All research coordinators and [name] will discuss data accuracy and management issues with the study PI. RAs will be in close communication with RPI investigators to ensure proper data analysis.

h) Provisions to Monitor the Data to Ensure the Safety of Subjects

The safety of subjects will be assured by constant monitoring of study protocols by:

MSH Principal Monitor, Study PI:
Last Name: [name]

	Protocol Name:	Systematic Programmed Illumination of Hospital Rooms to Prevent/Reduce Cancer-Related Fatigue during Autologous Stem Cell Transplantation for Multiple Myeloma
	Principal Investigator:	[name]; [contact]
	Primary Contact Name/Contact Info:	[name], [contact], [contact]
	Date Revised:	8/15/2019
	Study Number:	IF# 2517160 HS# 15-00777 GCO#: 15-2009

First Name: [name]
 Academic Title: Professor of Psychology
 Department: Oncological Sciences
 Mailing Address: [REDACTED], [name]
 [contact]
 [contact]
 E-mail: [contact]

MSH Additional Monitor, Team Members:

Last Name: [name]
 First Name: [name]
 Academic Title: Assistant Professor
 Department: Oncological Sciences
 Mailing Address: [REDACTED], [name]
 [contact]
 [contact]
 E-mail: [contact]

The proposed intervention is low-risk, and has been heavily informed by prior investigation by [name] and [name] . They are familiar with the intervention and its potential side effects, and will be able to provide consistent oversight of the project. Coherence of the collected data will be assessed on a yearly basis, while treatment compliance, adverse events, and patient expectancy/blinding will be assessed once every three months by [name], [name] and research coordinators. They will inform and alter study methods based on this information. Data management is described in section h above. If the study is put on hold, IRB will be informed of the change in study timeline.

i) Withdrawal of Subjects

Patients will be allowed to withdraw from the research at any time. They will also be allowed to skip any questions or questionnaires.

6) Risks to Subjects

There always exists the potential for loss of private information; however, all possible precautions will be set in place in order to prevent loss of confidentiality. See section 5h.

Other risks or side effects may include:

- Headache
- Nausea

	Protocol Name:	Systematic Programmed Illumination of Hospital Rooms to Prevent/Reduce Cancer-Related Fatigue during Autologous Stem Cell Transplantation for Multiple Myeloma
	Principal Investigator:	[name]; [contact]
	Primary Contact Name/Contact Info:	[name], [contact], [contact]
	Date Revised:	8/15/2019
	Study Number:	IF# 2517160 HS# 15-00777 GCO#: 15-2009

- If used incorrectly (e.g. such as staring directly into the light) it may cause eye discomfort or eye strain
- **Likelihood of Harm:** There will be minimal risk to the participants. Light levels will be much lower than those experienced when subjects are outdoors during a bright sunny day. The subjects will not be exposed to ultraviolet radiation.
- Light levels used in this experiment are lower than the levels produced by typical bright-light boxes (which is 10,000 lux) or produced at midday in a clear sunny day (about 100,000 lux). Using hazardous light exposure levels specified by the American Conference of Government Industrial Hygienists, one would need to be exposed to this light source for more than 10 hours continuously before it becomes a risk.
- Major research has not found increased risks of using light therapy for most major eye diseases. However, in the unlikely event the participant feels that the light is affecting their eyes or vision, they will be advised to contact the research team immediately.
- Previous research suggests that light therapy can improve the effectiveness of some antidepressant drugs. No evidence to date suggests that it decreases the effectiveness. If the participant is concerned about this, they will be advised to consult their physician.
- Completing questionnaires during the study may cause some distress or discomfort, however, past research has shown that such distress is usually minimal and transient.
- Wearing the light monitor (Daysimeter) and/or activity monitor (Actigraph) may cause discomfort. If this discomfort is unmanageable, the participant will be asked to report such discomfort to the research coordinator.
- Risks associated with blood draws: There is a minimal risk of pain, bruising, swelling, dizziness, or infection when blood is drawn from your arm. Some people feel dizzy or may faint during or after a blood draw. To minimize risk, blood for research purposes will only be drawn at the same time as routine clinical blood draws.

7) Provisions for Research Related Harm/Injury

The proposed project is a low-risk behavioral study. We will inform participants during the consent process that there is a chance that they will experience potential side effects of light therapy, e.g., sleep disturbance, headache, eyestrain, nausea, and hyperactivity, and in very rare instances, photic maculopathy, photophobia, hypomania, and suicidal ideation/suicide attempts have occurred (in those with pre-existing severe depression). They will be informed that such side effects are usually minimal if the light is positioned correctly and when they do occur, resolve within a few days. During the course of the protocol, if after 3 days the side effects persist, we will withdraw them from the study. Additionally, their care provider at the BMT clinic will be notified and refer the patient to a specialist if necessary. We will also follow up with those who discontinue the study due to side-effects and refer them to their care provider should symptoms persist even after discontinuation of the light exposure. Medical concerns will be billed according to other procedures occurring during hospitalization, since this is an inpatient study.

	Protocol Name:	Systematic Programmed Illumination of Hospital Rooms to Prevent/Reduce Cancer-Related Fatigue during Autologous Stem Cell Transplantation for Multiple Myeloma
	Principal Investigator:	[name]; [contact]
	Primary Contact Name/Contact Info:	[name], [contact], [contact]
	Date Revised:	8/15/2019
	Study Number:	IF# 2517160 HS# 15-00777 GCO#: 15-2009

We will also inform patients during the consent process that there is a chance participants will feel some distress or discomfort as a result of answering some questions asked during the study or completing the neuropsychological assessment. Participants will be assured that they can refuse to answer any questions or withdraw from the study at any time without penalty. Participants' psychological symptoms will be monitored throughout the study. If any participant expresses severe suicidal ideation, evidences acute or emergency psychiatric symptoms, or asks for psychiatric care, a referral will be made. The RA will be trained to identify participants who may be experiencing such problems and discuss them with [name] (a Ph.D.-level licensed clinical psychologist). The PI will be notified of any adverse participant reaction and psychiatric referral will be made, if necessary. If additional psychiatric care is warranted, participation in the study will be discontinued. Any participants presenting with physical complaints will be referred to their oncologist for evaluation so that the oncologist can rule out organic causes and/or make additional referrals, if needed. Participants who are assessed as having significant cognitive impairment and significant sleep dysfunction will also be referred to their oncologist for evaluation.

8) Potential Benefits to Subjects

Subjects may feel less fatigued after their transplant by undergoing daily sPI as a feature of their inpatient treatment. Subject fatigue may return after they stop sPI at the time of their medical discharge.

9) Provisions to Protect the Privacy Interests of Subjects

All study data collected will be also stored electronically. The data will be stored on a MSH network drive, accessible only to the PI and members of the research team. The data will be password protected. During data summarization and analysis, individual participants will be identified by code number only. No data identifying individual participants will be published or disclosed to third parties without prior consent of the participant. A list matching names with code numbers will be kept in a separate computer file and folder from the one where the data is stored.

If a participant agrees to participate in the study, all questionnaires will be labeled with the participants' study ID number, not their name and not their medical record number. Subjects will be informed that they can choose to not answer any questions that make them feel uncomfortable. Subjects will need to give study personnel their home addresses to which the study materials and questionnaires can be sent. This data will be kept private on the MSH network drive in a password protected spreadsheet. Subjects will mail back all study materials in a pre-paid envelope with an ID number and an MSH address as the return address.

Participants will provide the study team with a telephone number on which we can call them to administer questionnaires and help with any issues. If we need to leave a message, we will ensure that no confidential information or any information about the patient's study participation is revealed.

Subjects can withdraw from the study at any time or not answer questions they do not wish to address.

	Protocol Name:	Systematic Programmed Illumination of Hospital Rooms to Prevent/Reduce Cancer-Related Fatigue during Autologous Stem Cell Transplantation for Multiple Myeloma
	Principal Investigator:	[name]; [contact]
	Primary Contact Name/Contact Info:	[name], [contact], [contact]
	Date Revised:	8/15/2019
	Study Number:	IF# 2517160 HS# 15-00777 GCO#: 15-2009

10) Economic Impact on Subjects

We do not expect the subjects to incur any foreseeable costs through their participation in our study. We will be shipping all relevant study materials to each subject's home at our expense. Lights, actigraphs, and daysimeters will be provided to clients at no cost during the study. Blood draws at Mount Sinai will be scheduled on days of routine clinical visits, eliminating any additional transportation or cost to the subject.

11) Payments to Subjects

Study participants will receive a \$25 reimbursement for each time-point (study is divided into five time points – baseline 1, baseline 2, hospital stay, 1-month post and 3-months post). For a participant who completes the entire study this will come to a total of \$125 paid in two check installments of \$50 (or \$75 for the first installment if baseline 2 administered). This payment plan was established because subjects will not need to come into Mount Sinai specifically for the research study. Therefore, it will be more practical to request and send participants two checks, rather than five/six different checks throughout the duration of the study.

12) Consent Process

Informed consent will be obtained from participants in person before the collection of any data - Eligible patients will be contacted during their initial HSCT consult visit (time to transplant varies between patients) to MSH and given information on the study. The study coordinator will then administer the informed consent process. The RC will: describe the study, give the subject's time to read the consent form, allow the subjects to discuss their decision with whomever they like, allow the subjects to digest the information, and allow the patients to ask the member of the study team any additional questions they might have.

All consented participants will be informed about study procedures, extent of participation, and potential risks and that their participation is voluntary and will not jeopardize their relationship and participation in any activity they conduct or care that they receive at MSH. Participants will also be provided with a telephone number where they can call if they have any questions or concerns about the study or the consent form.

13) Process to Document Consent in Writing

We will be asking participants to sign the standard PPHS consent template.

14) Vulnerable Populations

Indicate specifically whether you will include (target) or exclude each of the following populations:

	Protocol Name:	Systematic Programmed Illumination of Hospital Rooms to Prevent/Reduce Cancer-Related Fatigue during Autologous Stem Cell Transplantation for Multiple Myeloma
	Principal Investigator:	[name]; [contact]
	Primary Contact Name/Contact Info:	[name], [contact], [contact]
	Date Revised:	8/15/2019
	Study Number:	IF# 2517160 HS# 15-00777 GCO#: 15-2009

Include	Exclude	Vulnerable Population Type
	X	Adults unable to consent
	X	Individuals who are not yet adults (e.g. infants, children, teenagers)
	X	Wards of the State (e.g. foster children)
	X	Pregnant women
	X	Prisoners

15) Multi-Site Human Research (Coordinating Center)

All information will be stored and managed by [name] at MSH. Actigraphs, Daysimeters, sampling materials, and questionnaires will be mailed between the participants and the study team at MSH. No identifying information will be included on the equipment and questionnaires will only include code numbers. MSH will send RPI the Actigraph and Daysimeter data via secure email. Blood samples will be analyzed at Mount Sinai's Human Immune Monitoring Core Shared Resource Facility. Urine samples will be analyzed at the laboratory at RPI LRC. Samples will only be identified by participants' study-ID numbers.

16) Community-Based Participatory Research

N/A

17) Sharing of Results with Subjects

If patients request information about the study results (i.e., whether light exposure was clinically effective in reducing cancer related fatigue), we will provide them with a copy of the publication that details the results.

18) External IRB Review History

N/A

19) Control of Drugs, Biologics, or Devices

Devices will be mailed to and from subjects via UPS. They are water resistant, and require no special care or attention from participants.

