Inflammatory response have been proposed to underlie CRF. There is an association between CRF among cancer patients and activation of pro-inflammatory signaling. For example, breast cancer survivors with persistent fatigue have elevated levels of markers associated with pro-inflammatory cytokine activity including Interleukin-1 receptor antagonist (IL-1ra), Interleukin-6 (IL-6), soluble tumor necrosis factor receptor type II (sTNF-RII), soluble intercellular adhesion molecule-1 (sICAM-1), and C-reactive protein (CRP). It has also been shown that chemotherapy leads to significant elevations in inflammation which is associated with increases in fatigue.

In the proposed preliminary feasibility research, sPI will deliver appropriately timed ambient, low-level, bluish-white light to patients during their hospital stay with floor lamps designed to deliver high circadian stimulation in the morning. We have selected cancer patients who are hospitalized for HSCT to treat MM because this population: (1) is relatively homogenous with a high prevalence of CRF, (2) can be studied prospectively across the course of HSCT, (3) permits careful monitoring of circadian rhythm entrainment through analysis of melatonin from urine obtained before, during and after HSCT, (4) regularly has blood drawn for clinical purposes and (5) allows assessment and control of confounding variables.

Preliminary research:

The proposed exploratory study builds on [name]’s, [name]’s, and [name]’s complementary areas of research. [name], [name] and colleagues’ ongoing investigation of BWL to treat CRF in cancer (including HSCT) survivors has formed the conceptual template for the proposed study and points to the potential importance of sPI in the prevention and treatment of CRF. In previous studies, they were able to retain 71% of participants, a retention rate that we also expect for the proposed protocol.

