	Protocol Name:	Systematic Programmed Illumination of Hospital Rooms to Prevent/Reduce Cancer-Related Fatigue during Autologous Stem Cell Transplantation for Multiple Myeloma
	Principal Investigator:	[name]; [contact]
	Primary Contact Name/Contact Info:	[name], [contact], [contact]
	Date Revised:	8/15/2019
	Study Number:	IF# 2517160 HS# 15-00777 GCO#: 15-2009

autologous HCST, the treating physician will discuss the study to their patient and inform them that they may be approached by a RA for participation. Additionally, a letter will be given to the patient, signed by the Director of the Multiple Myeloma program, introducing the study, team members, and to seek interest in participation. The following week, the RA will approach patients at their medical appointment at MSH in the months leading up to transplantation, unless the patient has expressed an unwillingness to participate. Physicians will inform RAs of those patients who have asked to not be approached for recruitment. The RC will then describe the study to determine their interest in participating, answer questions, and obtain Consent/HIPAA approval. A brief screening will subsequently be given to assess patient eligibility based on inclusion/exclusion criteria as listed in b) below. If there are any incidental findings during the screening and consent process, the subjects will be put in contact with a supervising licensed psychologist. The research team will look at each subject's CES-D scores at all timepoints to determine if they are at risk for severe depression. The protocol states that if a CES-D score is above 16, then the supervising psychologist will call the patient to determine if they need to be referred to get professional help regarding potential clinical depression. The BDI-II also can be used as a screener for depression. If a subject endorses suicidal ideation (by answering 2 or 3 for question 9, or scores in the severely depressed range between 29-63), then the supervising psychologist will also call the patient.

b) Inclusion and Exclusion Criteria

Our eligibility criteria includes:

Patients:

- Who will undergo their first autologous HSCT procedure as treatment for multiple myeloma
- AND:
- Who are currently 21 years of age or older
- English language proficient
- Able to provide informed consent

Exclusion criteria will be:

- Under age 21
- Previous HSCT procedure (autologous or allogeneic)Pregnancy

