- Eye Diseases which limit the ability of light to be processed (e.g., untreated cataracts, severe glaucoma, macular degeneration, blindness, pupil dilation problems or retina damage)
- Secondary cancer diagnosis within the last 5 years
- Severe sleep disorders (e.g., Narcolepsy)
- History of bipolar disorder or manic episodes (which is a contra-indication for light treatment)
- Severe psychological impairment (e.g., hospitalization for depressive episode in the past 12 months)
- Previous use of light therapy to alleviate fatigue or depressive symptoms

c) Number of Subjects

 Mount Sinai	Protocol Name:	Systematic Programmed Illumination of Hospital Rooms to Prevent/Reduce Cancer-Related Fatigue during Autologous Stem Cell Transplantation for Multiple Myeloma
	Principal Investigator:	[name]; [contact]
	Primary Contact Name/Contact Info:	[name], [contact], [contact]
	Date Revised:	8/15/2019
	Study Number:	IF# 2517160 HS# 15-00777 GCO#: 15-2009

For this feasibility study, we will recruit 60 participants drawn from the pool of upcoming HSCT admissions to treat MM at the MSH bone marrow transplant (BMT) clinic. Our previous research has demonstrated that at least 40% of this group either suffers from or will develop clinically significant fatigue related to cancer or its treatment.

d) Study Timelines

Total participation in this study is 16-18 weeks, and may vary by hospital admission, length of hospital stay, and expediency of returning study related materials.

Endpoints

The primary endpoints in the proposed study are: 1) Fatigue as measured by a simple Graphic Rating Scale, Multidimensional Fatigue FACIT Fatigue Scale, and The Pittsburgh Sleep Quality Index; 3) Depression as measured by the CES-D; 4) Quality of Life measured by the SF-36 scale; 5) Sleep/wake activity measured using an actigraph; and 7) Biological variables melatonin and inflammatory markers (i.e., IL-1ra, IL-6, MCP-1/CCL2, MIP-1a/CCL3, sTNFr1, sIL-6R, CRP) as obtained via urine and blood analysis.

The secondary endpoints include: 1) the amount of light received by the patient as measured by the Daysimeter; 2) treatment satisfaction using the FACIT-TS-G scale, and 3) Psychological moderators (e.g., emotions, symptom burden) that may affect for whom the treatment is effective.

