Acuity Lighting Brands will be providing the lighting fixtures in patient rooms at no cost. The fixtures will control all emitted wavelengths and provide both treatment and comparison conditions from the same fixture, as controlled by the investigators.

Methods: MM patients who will receive an autologous HSCT as part of their treatment plan will be recruited from MSH, and will be randomly assigned to either the BWL or the DWL conditions. Participants in both treatment arms will complete baseline 1 assessment at the time they are recruited. If Baseline 1 is completed more than two months before transplant participants will complete baseline 2 approximately one month before their transplant. After the baseline(s) assessment participants will be assessed: (A) during the inpatient hospital stay at day of transplant, day + 2, day + 7; (B) engraftment day 3 (most likely during week 2-3); (C) one month after hospital discharge; and (D) three months after hospital discharge. Outcome measures include standardized questionnaire measures of CRF, depression, sleep quality, and quality of life, as well as analysis of urinary melatonin and blood inflammatory marker levels at both outpatient and inpatient timepoints to monitor the biological processes believed to be influenced by sPI. This assessment schedule will allow us to evaluate the immediate and post-treatment benefits of the sPI treatment.

The proposed statistical analyses examine a number of related questions. The first consists of a comparison of the impact of the sPI exposure intervention to a comparison condition on CRF, depression, sleep quality, circadian rhythmicity, and quality of life using both the self-report and objective outcome measures (i.e. actigraphy data) in MM patients undergoing autologous HSCT. The second will examine the possible mediating role of depression, sleep quality, circadian activity rhythms, and fatigue on the effects of sPI. Lastly, the third will assess the feasibility and acceptability of an sPI intervention, actigraphy, urine melatonin analysis, and light exposure monitoring during HSCT. We will also look at possible co-moderators that may influence for whom the treatment works as defined by the list of additional measures we have included. In addition, we will explore whether the light treatment improves fatigue and depression through biological mediators analyzed in blood, i.e. inflammatory markers.

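### Persistent side effects take a patient out of the study, not only off the light, so later outcome visits are lost that could be kept

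*Combined protocol and SAP*

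**What the plan says.** Section 7 lists possible side effects of light therapy, with sleep disturbance first among them, and then gives the rule: "During the course of the protocol, if after 3 days the side effects persist, we will withdraw them from the study". What follows is clinical: the transplant clinic's care provider is told, and "We will also follow up with those who discontinue the study due to side-effects and refer them to their care provider". Section 5i (Withdrawal of Subjects) covers only withdrawal by the patient's own choice and skipped questions. No section provides for outcome assessment after a stop under Section 7.

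A second rule in Section 7 concerns psychiatric need: "If additional psychiatric care is warranted, participation in the study will be discontinued".

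Section 5e (Methods) schedules assessments on the day of transplant, day +2, day +7 and engraftment day 3, then one and three months after discharge. Hypothesis 1b in Section 1 rests on the last two. Section 5f adds two urine collections and four blood draws. On retention, Section 2 says of the team's previous studies that "they were able to retain 71% of participants, a retention rate that we also expect for the proposed protocol".

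The Data Analysis text names fatigue as the primary outcome and depression, sleep and circadian rhythms among the secondary ones. It plans mixed models with time, covariates, group and a random intercept. It does not say how withdrawn patients are handled and plans no sensitivity analysis for missing data.

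**The concern.** Stopping a treatment and stopping observation are separate decisions, and the Section 7 rule joins them. The light should stop when it is not tolerated. Nothing about intolerance requires the questionnaires, the actigraph or the follow-up visits to stop as well.

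The patients lost this way are not a random subset. Sleep disturbance can be both the reason for the stop and part of what Aim 1 measures. One arm receives 1300 lux and the other 90 lux, so side effects of the light could occur at different rates in the two arms. Missing data that depend on both outcome and arm can bias the comparison.

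The study is also meant to supply effect sizes for a larger trial and to judge tolerability. Patients who could not tolerate the light are informative for both purposes.

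**Working it through.** **1. Does the text end outcome collection?** The rule removes patients from the study. The follow-up sentence after it concerns symptoms and referral. Section 5i and the Data Analysis text add nothing on continued assessment. Loss of later data is therefore the ordinary reading, though it is an inference and not an explicit statement.

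**2. What is lost, by time of stop.** There are 6 post-baseline assessments (Section 5e). The 4 blood draws are at admission, engraftment day 3, about one month and about three months (Section 5f). The 2 urine collections are at baseline 1 and engraftment day 3 (Section 5f). The 2 Hypothesis 1b visits are at one and three months. The loss is everything after the last item completed.

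| Stop falls between | Assessments lost (of 6) | Blood lost (of 4) | Urine lost (of 2) | Hypothesis 1b visits lost (of 2) |
|---|---|---|---|---|
| day +2 and day +7 | 4 | 3 | 1 | 2 |
| day +7 and engraftment day 3 | 3 | 3 | 1 | 2 |
| engraftment day 3 and one month | 2 | 2 | 0 | 2 |
| one and three months (psychiatric rule) | 1 | 1 | 0 | 1 |

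The urine collection in the first two rows is the only one made during treatment.

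**3. Retention.** At the plan's 71%, 0.71 × 60 = 42.6 patients remain and 17.4 are lost from all causes. Each patient kept who would otherwise be lost adds 1/42.6 = 2.3% to the number remaining. The documents do not say how many of the 17 would be lost through Section 7.

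**4. Precision.** For a two-group difference in means, in SD units, the 95% CI half-width is 1.96 × √(4/N).
- N = 60: 1.96 × √(4/60) = 0.506
- N = 42.6: 1.96 × √(4/42.6) = 0.601

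**5. Scale of bias per excess stop.** Suppose a stopped patient would later have scored D worse than the rest of the arm, in SD units. Losing that patient from an arm of 30 shifts the arm's mean by D/30 before any recovery by the model. D is an assumption, taken as 0.5 to 1.
- D = 0.5: 0.5/30 = 0.017
- D = 1: 1/30 = 0.033
- Data missing at random given the model: 0

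At most, one excess stop is worth 0.033/0.506 = 6.5% of the CI half-width with 60 patients, or 0.033/0.601 = 5.5% with 43. Total bias cannot be computed, because the documents give no stopping rates by arm.

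**6. What the mixed model covers.** It protects if data are missing at random given its terms and the patient's earlier scores on the same outcome. A stop for sleep disturbance is covered as far as the recorded sleep scores already show it. Deterioration between recorded assessments is not covered.

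**The case against.** The case on the other side is substantial, and most of it limits the point without removing it.

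- **The wording is loose.** The same paragraph of Section 7 also speaks of discontinuing the light exposure, and the consent pages are not available here. A reader might take it as stated fact that data collection stops. The documents do not say so outright. It is the natural reading, and nothing in them contradicts it.
- **Sleep problems alone do not end participation.** Section 7 refers patients with significant sleep dysfunction to the oncologist and does not mention withdrawal. Only a persistent side effect of the light triggers the rule. The overlap with the sleep outcomes is real but narrower than it first appears.
- **A CES-D score is not a stopping trigger.** A reader might infer that it is, because Section 5a says that "if a CES-D score is above 16, then the supervising psychologist will call the patient to determine if they need to be referred", and the endpoint list includes "3) Depression as measured by the CES-D". The documents do not support that. The score leads to a call, the call may lead to a referral, and participation ends only on a separate clinical judgment that more psychiatric care is needed. If a recorded CES-D score did drive a stop, it would be an observed value in the depression model, which favours missing at random for that outcome.
- **Fatigue, the primary outcome, is not a listed side effect.** The daily inpatient fatigue line scale, if analysed, also documents fatigue up to the stop.
- **Few stops are likely.** Section 5b excludes bipolar history, recent hospitalisation for depression, severe sleep disorders and relevant eye disease. Section 7 describes side effects as usually minimal.
- **Some monitoring exists.** The safety endpoint text follows patients who choose to stop because they find the light unacceptable, and Section 5h reviews compliance and adverse events quarterly. Neither collects outcomes after a Section 7 stop or reports stops by arm.

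What stands is that the side-effect rule, followed as written, discards later outcome data without need.

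**Conclusion.** The point holds as a cheap improvement. A patient stopped in hospital for persistent side effects would lose both Hypothesis 1b visits and, if stopped before engraftment day 3, the only on-treatment urine sample. The loss may be related to sleep outcomes and to arm.

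A reader might go further and infer a material bias in favour of the bright-light arm, or blame the expected 29% loss on this rule. The documents support neither. They give no stopping rates by arm or by reason, so direction and size are unknown. The 71% retention figure comes from previous studies and covers all causes. The 0 to 0.03 SD per excess stop rests on the assumed gap of 0.5 to 1 SD and is for scale only. With few stops expected, bias is probably small.

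The psychiatric rule is secondary. The light ends at discharge (Section 8), so a psychiatric stop after that removes no exposure and ends only assessment. Section 7 nevertheless recognises that questionnaires can distress patients, and ending participation on those grounds is a defensible safety choice.

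**What to change.** Keep the clinical stopping triggers. In the Section 7 side-effect rule, replace withdrawal from the study with stopping the light. Continue the scheduled questionnaires, actigraphy, engraftment-day urine and blood, and one- and three-month assessments unless the patient withdraws consent. In Data Analysis, state that these patients are analysed in their assigned arm, and report the number of stops by arm and by reason.

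For the psychiatric rule, any continued follow-up should at most be optional and reduced, with the supervising psychologist's agreement and the patient's consent. It may recover little data.

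The cost is a change to protocol and consent wording. The assessments are already scheduled, questionnaires can go by mail or telephone (Section 9), and research blood is drawn with routine clinical blood (Section 5f). Staff already follow up patients who stop for side effects (Section 7). The downside is a small assessment burden for a few patients.
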